6.5. Other Displays of Sperm/Semen Data

6.5.1. Treatment-Sequence Semen Displays (Week 26/OL Week 13 and Extension Phase)

The proportion of subjects with a $\geq 50\%$ decrease from baseline in sperm concentration will be presented by treatment sequence and analysis visit. An exact 95% CI for the proportion of subjects with a $\geq 50\%$ decrease from baseline in sperm concentration at Week 26/OL Week 13 within treatment sequence will be presented based on the Clopper-Pearson method.

Descriptive statistics will be presented at Baseline, Week 26/OL Week 13 and subsequent visits by actual treatment sequence to explore the confounding effects of IBD response to treatment. A 95% distribution-free CI on the median change and percentage change from baseline in sperm/semen parameters at Week 26/OL Week 13 will be constructed by treatment sequence using the CIPCTLDF option in PROC UNIVARIATE in SAS. Study days will be used for assignment of analysis visit windows for subjects who stayed on randomized drug throughout study and for subjects who started on double-blind filgotinib and switched to open-label filgotinib. For subjects who switched from placebo to open-label filgotinib, days on open-label filgotinib will be used to assign analysis visit windows. Week 26 for the first 3 treatment

sequences will be displayed along-side OL Week 13 for placebo to OL filgotinib group; Week 39 alongside OL Week 26 for placebo to OL filgotinib group, etc. to align with the originally planned study weeks, but using the at/after Protocol Amendment 3 visit schedule to ensure that subjects who switched from placebo to open-label filgotinib had at least 85 days on filgotinib prior to their first semen collection while on filgotinib treatment (eg, a full sperm cycle).

A cumulative distribution plot for percentage change from baseline in sperm concentration at the Week 26/OL Week 13 visit will be constructed by treatment sequence for subjects who are still on study drug at Week 26/OL Week 13.

The number of days on filgotinib at the time of the first of 2 semen assessments at the Week 26/Open-Label Week 13 analysis visit will be summarized by treatment sequence for subjects with evaluable samples in the analysis visit window.

A listing of subjects in the placebo to open-label filgotinib treatment sequence who had nominal visits for Week 26 or Open-Label Week 13 that were outside of the analysis visit window for OL Week 13 will be provided—primarily to assess the number of subjects who were on original/ Protocol Amendment 1 visit schedule and did not have sufficient exposure (minimum of 85 days) on open-label filgotinib at the time of their first collection to fall within the Open-Label Week 13 analysis visit window

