Part B (After Week 13 through Week 26 Study Visit)

(Appendix 11 and Figure 3-3)

In Part B, all subjects will continue blinded study drug for up to an additional 13 weeks. Subjects may experience Disease Worsening (see Definition of Terms) of their underlying IBD at any time during blinded study drug treatment (after Week 13 through Week 26). If Disease Worsening is confirmed, sperm parameters will be evaluated to determine whether a pre-specified decrease threshold has been met prior to a study drug change (changing from blinded study drug to OL filgotinib). Based upon the sperm parameters at this time point, subjects may follow one of the following pathways:

- All subjects whose sperm parameters meet a pre-specified decrease threshold, regardless of IBD response status, will discontinue blinded study drug and enter the Monitoring Phase.
- Subjects who experience Disease Worsening after Week 13 and prior to Week 26, and whose sperm parameters do not meet a pre-specified decrease threshold will discontinue blinded study drug and commence OL filgotinib.
- Subjects who do not experience Disease Worsening, and are Responders at Week 26, and whose sperm parameters do not meet a pre-specified decrease threshold, will continue blinded study drug as part of the Long Term Extension (LTE).
- Subjects who do not experience Disease Worsening, but are Non-responders at Week 26, and whose sperm parameters do not meet a pre-specified decrease threshold, will discontinue blinded study drug and complete a safety follow-up visit 30 days after last study drug dose.

Open-Label Filgotinib Phase (Open-Label Day 1 through Open-Label Week 13 Study Visit)

(Appendix 11 and Figure 3-4)

After exposure to 13 weeks of OL filgotinib, the subject's IBD response status will be determined and sperm parameters will be evaluated to determine whether a pre-specified decrease threshold has been met. Subjects will be evaluated during this phase as follows:

- All subjects whose sperm parameters meet a pre-specified decrease threshold, regardless of Responder status, will discontinue OL filgotinib, complete a safety follow-up visit 30 days after last study drug dose, and enter the Monitoring Phase.

- Subjects who experience Disease Worsening and whose sperm parameters do not meet a pre-specified decrease threshold will discontinue OL filgotinib, complete Early Termination (ET) and a safety follow-up visit 30 days after last study drug dose.

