3.4. Disease Worsening Criteria

Subjects meeting the following Disease Worsening criteria, evaluated after Week 13 through Week 26, must be discontinued from blinded treatment. These subjects will be offered the option to commence OL filgotinib 200 mg once daily, as long as they have not experienced a decrease of $\geq 50\%$ from baseline in sperm concentration, and/or motility, and/or morphology.

Upon confirmation of Disease Worsening and before switching to the OL Filgotinib Phase, 2 semen samples will be collected. Disease Worsening is confirmed at the time of the second consecutive visit. If the second Disease Worsening visit occurs during the 14-day semen

collection window for the Week 13 or Week 26 Study Visit, the routine Week 13 or Week 26 semen collection will suffice.

Disease Worsening assessments will be driven by the patient history, physical and laboratory examinations and are based on the following criteria:

For subjects with UC, Disease Worsening is defined by a partial MCS after Week 13 consisting of:

- An increase of ≥ 3 points to at least 5 points from the Week 13 value on 2 consecutive visits, OR
- An increase to 9 points from the Week 13 value on 2 consecutive visits, if the Week 13 value was > 6 points

For subjects with CD, Disease Worsening is defined by a total CDAI score after Week 13 consisting of:

- A score ≥ 220 on 2 consecutive visits, AND
- An increase of ≥ 100 points from the Week 13 value on 2 consecutive visits

For all subjects, Disease Worsening is further defined by:

- Disease Worsening to the extent that the subject requires medications prohibited by the study (at investigator's discretion, with discussion with the medical monitor or designee if feasible); these subjects do not qualify to receive OL filgotinib 200 mg once daily.

Disease Worsening visits may include Unscheduled Visits (eg, a Study Visit followed by an Unscheduled Visit, or 2 sequential Unscheduled Visits after Week 13).

In the LTE, subjects who meet Disease Worsening criteria (per above criteria), or have Disease Worsening per investigator judgment, should be discontinued from study drug. These subjects should complete an ET visit (which includes semen collection), followed by a routine safety follow-up visit 30 days after the last dose of study drug.

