3.2. Subject Grouping

For analyses based on the All Randomized and ITT Semen Analysis Sets, subjects will be grouped according to their randomized treatment. For all other analysis sets, subjects will be grouped according to the actual treatment received. The actual treatment received will differ from the randomized treatment only when the actual treatment differs from randomized treatment for the entire treatment duration of the study drug administration period.

The following subject groupings will be applied to the semen and hormone data according to the actual treatment received:

- For the double-blind treatment period, data from subjects who took double-blind treatment will be summarized by treatment group (ie, filgotinib 200 mg and placebo).
- Semen and hormone data collected after Week 13 will be summarized by treatment sequence (ie, double-blind filgotinib, double-blind filgotinib to open-label filgotinib, double-blind placebo, and double-blind placebo to open-label filgotinib) for subjects with baseline and ≥ 1 visit at/after Week 26. Analysis visit windows for the double-blind placebo to open-label filgotinib group will be windowed from the first dose date of open-label filgotinib and will be 13-weeks prior to those who remained on original treatment. All other treatment sequences will have analysis visit windows assigned based on days from first dose of double-blind study drug.

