Week 221	1548	1535	≥ 1548
FU-4*	Last Dose Date any study drug + 30 days	Last Dose Date any study drug + 8 days	Last Dose Date any study drug + 35 days

Note: Primary analysis includes data up to first dose date of open-label filgotinib (if non-missing) or to last dose date of double-blind drug + 7 days (for those who do not switch to open-label filgotinib).

Secondary analysis includes all “on-treatment” data up to the last dose date of any study drug + 7 days.

*FU-4 visit for subjects who have stopped all study drugs and had a 30-day safety FU visit ± 5 days will be displayed in listings only.

Table 3-4. Analysis Visit Windows for On-Treatment Semen Parameters

Analysis Visit	Nominal Day (Study Day)	Lower Limit (Study Day)	Upper Limit (Study Day)
Baseline	1	None	1
Week 13	92	85	112
Week 26	183	170	260
Week 39	274	261	351
Week 52	365	352	442
Week 65	456	443	533
Week 78	547	534	624
Week 91	638	625	715
Week 104	729	716	806
Week 117	820	807	897
Week 130	911	898	988
Week 143	1002	989	1079
Week 156	1093	1080	1170
Week 169	1184	1171	1261
Week 182	1275	1262	1352
Week 195	1366	1353	1443
Week 208	1457	1444	1534
Week 221	1548	1535	≥ 1548

Note: Primary analysis includes data up to first dose date of open-label filgotinib (if non-missing) or to last dose date of double-blind drug + 7 days (for those who do not switch to open-label filgotinib).

Secondary analysis includes all “on-treatment” data up to the last dose date of any study drug + 7 days.

Table 3-5. Analysis Visit Windows for Semen Parameters in Monitoring Phase (Calculated from Last Dose Date of Any Study Drug)

Analysis Visit	Nominal Day (FU Day)	Lower Limit (FU Day)	Upper Limit (FU Day)
MP Week 13	91	8	104
MP Week 26	182	105	195
MP Week 39	273	196	286
MP Week 52	364	287	377

MP = Monitoring Phase; FU = Follow-Up.

NOTE: All visit windows for monitoring phase will be calculated from last dose date of any study drug.

FU Day = visit date – last dose date of any study drug.

Investigator Assessment of ECG Visit Assignment

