6.5.2. Pre-Specified Sperm Decrease Threshold Criteria and Confirmed Semen Abnormalities

Subjects who met a pre-specified sperm decrease threshold criteria (a $\geq 50\%$ decrease in sperm concentration and/or motility and/or morphology) were to stop study drug and begin a standard of care regimen selected by the investigator in accordance with the protocol and be followed off study drug to evaluate for reversibility criteria.

A “confirmed semen abnormality” as defined by Jarvi and colleagues {Jarvi 2008} reflects the presence of abnormal sperm parameters potentially associated with decreased male fertility; the criterion is met when one or more of the following are observed: a sperm concentration < 5 M/mL, or sperm motility $< 20\%$, or a percent normal sperm morphology of $< 10\%$.

The number and proportion of subjects meeting any of the pre-specified sperm decrease thresholds (from the baseline value [mean of 2 evaluable semen collections at screening]) or any of the components of a confirmed semen abnormality (mean of 2 evaluable samples at a study visit) at the double-blind Week 13 (primary endpoint) visit will be displayed by double-blind treatment group:

Sperm Decrease Criteria

- $\geq 50\%$ decrease in sperm concentration
- $\geq 50\%$ decrease in sperm total motility
- $\geq 50\%$ decrease in sperm morphology [% normal] (WHO 1992 criteria)
- $\geq 50\%$ decrease in sperm concentration and ($\geq 50\%$ decrease in total motility and/or morphology [% normal] at the same visit)

Confirmed Semen Abnormality Criteria (as defined by Jarvi et al)

- Sperm concentration < 5 M/mL
- Sperm total motility $< 20\%$
- Sperm morphology (% normal) $< 10\%$
- Confirmed Semen Abnormality (Sperm concentration < 5 M/mL or sperm total motility $< 20\%$ or sperm morphology [% normal] $< 10\%$ at the same visit)

The number and proportion of subjects meeting any of the pre-specified sperm decrease thresholds or components of a confirmed semen abnormality (as described above) at the Week 26/OL Week 13 analysis visit and at/after the Week 39/OL Week 26 visit will be displayed by treatment sequence. Treatment sequences to be presented are:

- double-blind (DB) filgotinib
- DB filgotinib to open-label (OL) filgotinib
- DB placebo
- DB placebo to OL filgotinib

A listing of subjects who met any of the components of a confirmed semen abnormality will be provided.

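### In the Week 26/OL Week 13 treatment-sequence displays, Disease Worsening semen pairs first dated Study Day 170 to 260 are sorted into rows partly by their own result

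*SAP*

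**What the plan says.** Protocol 3.4 sets the timing of the sample: "Upon confirmation of Disease Worsening and before switching to the OL Filgotinib Phase, 2 semen samples will be collected". If the confirming visit falls in the routine collection window, "the routine Week 13 or Week 26 semen collection will suffice".

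The result then sets the path. In the Protocol Synopsis (Part B), men who meet a decrease threshold (concentration, motility or morphology), "regardless of IBD response status, will discontinue blinded study drug and enter the Monitoring Phase". Men with Disease Worsening and no threshold decrease go on to OL filgotinib.

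SAP 3.2 groups semen data after Week 13 by the sequence actually received: DB filgotinib, DB filgotinib to OL, DB placebo, and DB placebo to OL. The clocks differ: "Analysis visit windows for the double-blind placebo to open-label filgotinib group will be windowed from the first dose date of open-label filgotinib", while the other three sequences count days from the first double-blind dose. SAP Table 3-4 puts Week 26 at Study Days 170 to 260 and Week 39 at Days 261 to 351. Days 113 to 169 belong to no window. SAP 3.7.3 dates a pair by its first valid sample.

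The affected displays are those of SAP 6.5.1 and 6.5.2. SAP 6.5.1 plans: "Descriptive statistics will be presented at Baseline, Week 26/OL Week 13 and subsequent visits by actual treatment sequence". In the same section, an exact interval for the proportion with a concentration decrease "within treatment sequence will be presented based on the Clopper-Pearson method", together with median intervals and a cumulative distribution plot. In 6.5.2, threshold counts "at the Week 26/OL Week 13 analysis visit and at/after the Week 39/OL Week 26 visit will be displayed by treatment sequence".

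**The concern.** A row in a table of semen outcomes should not be chosen by the semen outcome it reports. Here a pair collected on blinded drug can be filed under a double-blind sequence if it shows a decrease and under an OL sequence if it does not. The stated aim of the 6.5.1 displays is to explore confounding by IBD response. That explains grouping men by sequence, but it does not address sorting on the semen result.

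At stake are the only Week 26 proportions in the SAP with exact intervals, and the only Week 26 cumulative plot, in a study whose purpose is testicular safety. If Disease Worsening were more common in one arm, the two double-blind rows would be distorted by different amounts.

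**Working it through.** The plan states no figure for these displays. Its sample-size figure, 200/(1 − 0.2) = 250, reproduces but has no bearing here.

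**Step 1: which pairs are affected.** Inputs are Table 3-4 and the rule that OL Week 13 follows 13 weeks (91 days) of OL drug.

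- Pair first dated Day 170 or later, up to Day 260: it is in the Week 26 window. OL drug starts on Day 171 at the earliest, so under the current visit schedule the OL Week 13 pair falls on Day 171 + 91 = 262 at the earliest, which is Week 39. For a filgotinib-to-OL man the pre-switch pair is then his only Week 26 value.
- Pair first dated Days 113 to 169: no window, so it is not shown in any row.
- Placebo-to-OL: the pre-switch pair precedes the OL clock and is not shown as OL Week 13. The man only leaves the DB placebo denominator.

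**Step 2: double-blind rows.** Take N men with a double-blind pair in the Week 26 window. Let p be the true decrease rate, w the share with an in-window Disease Worsening pair, and e the share of no-decrease Disease Worsening men who actually switch. All Np decreases stay, and N·w·(1 − p)·e event-free men leave:

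row proportion = p / (1 − w(1 − p)e)

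Removing only event-free men raises the proportion whatever the rates. The size depends on p, w and e, none of which the documents give. The figures below assume p is the same in men with and without Disease Worsening.

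| p | w | e | Row shows |
|---|---|---|---|
| 8% | 5% | 1 | 0.08/0.954 = 8.4% |
| 8% | 10% | 1 | 0.08/0.908 = 8.8% |
| 8% | 20% | 1 | 0.08/0.816 = 9.8% |
| 8% | 30% | 1 | 0.08/0.724 = 11.0% |
| 8% | 20% | 0.8 | 0.08/0.8528 = 9.4% |
| 5% | 30% | 1 | 0.05/0.715 = 7.0% |
| 15% | 30% | 1 | 0.15/0.745 = 20.1% |

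**Step 3: filgotinib-to-OL row.** If a share m of its Week 26 values are pre-switch pairs, the row shows p(1 − m). With p = 10% and m = 10%, 25% or 50% (assumed), it shows 9.0%, 7.5% or 5.0%.

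**Step 4: unequal Disease Worsening.** With both true rates 10%, w = 10% on filgotinib and 30% on placebo (assumed, e = 1), the double-blind rows show 0.10/0.91 = 11.0% and 0.10/0.73 = 13.7%. That is a spurious difference of −2.7 points.

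**Step 5: counts for one filgotinib arm (assumed).** Take 50 men with a Week 26 double-blind pair, 4 decreases, and 10 Disease Worsening men of whom 1 has a decrease. By treatment at collection the result is 4/50 = 8.0%. As planned it is 4/(50 − 9) = 4/41 = 9.8%, and the other 9 men enter the filgotinib-to-OL row as 0/9.

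**The case against.** The strongest reply is that an unsorted display already exists. SAP 6.2 presents the Week 26 secondary endpoint by double-blind group, with a count of concentration decreases at any time up to Week 26. The Table 3-4 note keeps data up to the first OL dose, so pre-switch pairs stay in their arm there. This stands, and it limits the damage to 6.5.1 and 6.5.2.

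The affected group may also be small. Disease Worsening needs two consecutive qualifying visits after Week 13, and the only scheduled Part B visits are Weeks 20 and 26. An in-window pair therefore comes from confirmation at Week 26 or from unscheduled visits. The sort is incomplete too: OL is optional, men needing prohibited medication do not qualify, and men with only a motility or morphology decrease stay in the double-blind rows without a concentration event. In the count example the exact intervals, 2.2% to 19.2% and 2.7% to 23.1%, overlap almost entirely. All of this bears on size, not on direction.

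The displays are descriptive, with intervals within sequence and no planned comparison between sequences. A reader might infer that the sort makes filgotinib look safer. The documents do not support that: it would need more Disease Worsening on placebo, for which no rate is given.

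A reader might also infer that filing a late switcher's OL Week 13 pair under Week 39 contradicts SAP 2.4. It does not. That section sets when an analysis is triggered, not how this table counts. The alignment is deliberate, since filgotinib-to-OL men are on filgotinib throughout.

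Finally, SAP 3.1.2, where the semen analysis sets are defined, was not in the text read. A rule there on which pairs enter the displays cannot be excluded.

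**Conclusion.** The point holds for Disease Worsening pairs first dated Study Day 170 to 260. In the sequence displays the DB filgotinib and DB placebo proportions at Week 26 are biased upward. The DB filgotinib to OL row is biased downward, because its pre-switch pairs are below threshold by construction.

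It would be too strong to say that every Disease Worsening sample is sorted this way, or that both OL rows are distorted. Pairs on Days 113 to 169 fall in no window, and the placebo-to-OL row runs on the OL clock. The Week 13 primary analysis and the Week 26 display by double-blind group are not affected.

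Size cannot be fixed from the documents. At an assumed true rate of 8%, a double-blind row shows about 8.4% to 11.0% for an assumed in-window Disease Worsening share of 5% to 30% if every no-decrease man switches, and less if some do not. The change is worth making because the bias is avoidable and costs little to remove.

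**What to change.** In SAP 3.2, 6.5.1 and 6.5.2, state that every semen pair collected before the first OL dose is tabulated under the double-blind treatment the man was taking at collection, whatever he did next. This is the data cut already in the Table 3-4 note. State also that a pre-OL pair is never the Week 26 value of an OL sequence.

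Keep the double-blind clock for filgotinib-to-OL men. Moving them to an OL clock would break the planned exposure alignment. A late switcher's first on-OL pair then appears under Week 39.

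The protocol should also be reconciled with itself. The Part B text in the Synopsis and Section 3 gives the OL route for Disease Worsening before Week 26, whereas Sections 3.3.2 and 3.4 extend it through Week 26. Confirmation at the Week 26 visit is the main scheduled in-window route, so the number of affected men depends on which reading applies.

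The cost is SAP wording and a change to the visit-assignment program, with no new data. The downside is that one man can appear in a double-blind row at Week 26 and in an OL row later, which needs a footnote. The SAP Introduction already provides for changes after finalization to be documented in the clinical study report.

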6.5.2. Pre-Specified Sperm Decrease Threshold Criteria and Confirmed Semen Abnormalities

Subjects who met a pre-specified sperm decrease threshold criteria (a $\geq 50\%$ decrease in sperm concentration and/or motility and/or morphology) were to stop study drug and begin a standard of care regimen selected by the investigator in accordance with the protocol and be followed off study drug to evaluate for reversibility criteria.

A “confirmed semen abnormality” as defined by Jarvi and colleagues {Jarvi 2008} reflects the presence of abnormal sperm parameters potentially associated with decreased male fertility; the criterion is met when one or more of the following are observed: a sperm concentration < 5 M/mL, or sperm motility $< 20\%$, or a percent normal sperm morphology of $< 10\%$.

The number and proportion of subjects meeting any of the pre-specified sperm decrease thresholds (from the baseline value [mean of 2 evaluable semen collections at screening]) or any of the components of a confirmed semen abnormality (mean of 2 evaluable samples at a study visit) at the double-blind Week 13 (primary endpoint) visit will be displayed by double-blind treatment group:

Sperm Decrease Criteria

- $\geq 50\%$ decrease in sperm concentration
- $\geq 50\%$ decrease in sperm total motility
- $\geq 50\%$ decrease in sperm morphology [% normal] (WHO 1992 criteria)
- $\geq 50\%$ decrease in sperm concentration and ($\geq 50\%$ decrease in total motility and/or morphology [% normal] at the same visit)

Confirmed Semen Abnormality Criteria (as defined by Jarvi et al)

- Sperm concentration < 5 M/mL
- Sperm total motility $< 20\%$
- Sperm morphology (% normal) $< 10\%$
- Confirmed Semen Abnormality (Sperm concentration < 5 M/mL or sperm total motility $< 20\%$ or sperm morphology [% normal] $< 10\%$ at the same visit)

The number and proportion of subjects meeting any of the pre-specified sperm decrease thresholds or components of a confirmed semen abnormality (as described above) at the Week 26/OL Week 13 analysis visit and at/after the Week 39/OL Week 26 visit will be displayed by treatment sequence. Treatment sequences to be presented are:

- double-blind (DB) filgotinib
- DB filgotinib to open-label (OL) filgotinib
- DB placebo
- DB placebo to OL filgotinib

A listing of subjects who met any of the components of a confirmed semen abnormality will be provided.

